3. INTRODUCTION

3.1. Preface

This document presents a statistical analysis plan (SAP) for aTyr Pharma, Inc. Protocol ATYR1923-C-002 (*A Randomized, Double-Blind, Placebo-Controlled Multiple Ascending Dose Study of Intravenous ATYR1923 in Patients with Pulmonary Sarcoidosis*).

Reference materials for this statistical plan include the Protocol Version 3.0 dated 25Sep2020 and Case Report Forms (Version 15.0, 9APR2021).

The SAP described hereafter is an *a priori* plan. The SAP will be finalized and approved prior to unblinding of any study data. Statistical programming may occur as study data accumulate in order to have analysis programs ready at the time the study finishes. In such an event, arbitrary treatment group assignments must be randomly linked to patients, effectively rendering any output of programs meaningless.

For the reasons stated here the conduct of the study in the field is considered to be independent of any study outcome that might materialize upon enactment of the currently proposed statistical plan.

3.2. Purpose of Analyses

The purposes of the planned analyses described in this SAP are to evaluate the safety and tolerability of multiple ascending intravenous (IV) doses of ATYR1923 in patients with pulmonary sarcoidosis. Results from the analyses completed will be included in the final clinical study report for ATYR1923, and may also be utilized for regulatory submissions, manuscripts, or other clinical development activities.

Post-hoc exploratory analyses not identified in this SAP may be performed to further examine the study data. These analyses will be clearly identified, where appropriate, in the final clinical study report. Additional analyses not prospectively identified in this SAP may also be completed for publications, or regulatory or funding inquiries. These analyses, if performed, may not be reported in the clinical study report, but will be fully documented in the document containing the additional analyses.

3.3. Summary of Statistical Analysis Changes to the Protocol

The PK Concentration Parameter Analysis Set included in the protocol, Section 10.1.1.4, is not included in this SAP. Instead, an Efficacy Evaluable Set has been added. The Intent to Treat (ITT) Analysis Set is included in the Protocol, Section 10.1.1.1. However, due to the possibility of subjects who have been randomized but not dosed, a modified Intent-to-Treat (mITT) population is used in the SAP.

aTyr Pharma, Inc.
Study ATYR1923-C-002 Statistical Analysis Plan
IND#: 133692

FINAL Version 1.0
2021-08-02

The first secondary endpoint specified in the protocol specifies the following.

- Total cumulative steroid dose administered over the primary study period (Day 1 through Week 24) by treatment cohort

During planning of this analysis, it was brought to attention that subjects may be dosed for different periods of time, and visits may occur at different study days for different subjects due to scheduling conflicts. Therefore, a time adjusted AUC will be used to examine OCS use.

In the protocol secondary endpoints below are specified for Week 24 visit.

- Total cumulative steroid dose administered over the primary study period (Day 1 through Week 24) by treatment cohort
- Number of patients who achieve the targeted tapered dose of prednisone 5 mg/day (or equivalent) and maintain it through Week 24 by treatment cohort

In light of the half-life of the investigational product, it was decided that the endpoints will be examined for the end of dosing period instead. The end of dosing period is defined as 30 days after the last dose.

In addition, due to protocol prescribed taper prior to Day 51, an additional period, Day 51 through end of dosing interval, will also be examined, together with Day 1 through end of dosing interval.

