- 16. Patient has received a live vaccination within 8 weeks before Day 1 or inoculation with a live vaccine is planned during study participation.
- 17. Jo-1 Ab levels >7 U/mL at Screening, or past history of Jo-1 Ab positivity.

- 18. Any other condition or circumstance that, in the opinion of the investigator, would be likely to prevent adequate compliance with the study protocol.
- 19. Significant and/or acute illness (eg, change in pulmonary status, infection requiring antibiotics) within 5 days prior to (the first) drug administration that may impact safety assessments, in the opinion of the Investigator.

Test Products, Doses, and Mode of Administration:

ATYR1923 (or matching Placebo) will be provided in vials of 25 mg/mL strength. Placebo infusion will be identical in appearance to the active drug to maintain blinding.

All investigational product will be administered via an IV infusion over a 60-minute duration.

For the preparation of the ATYR1923 dose levels the weight of the patients at Screening will be used.

Duration of Screening, Treatment and Follow-up:

The duration of patient participation is up to 28 weeks, including:

- A Screening period for up to 4 weeks in duration.
- A 20-week treatment period with six (6) study drug infusions administered every 4 weeks.
- An EOS visit, 4 weeks after last study drug infusion.

Note that patients with elevated confirmed positive Jo-1 antibody titers or who have ongoing study drug-related treatment-emergent adverse events (TEAEs) at Week 24/EOS will continue to be followed until resolution or determined by the Investigator to be stable (eg, by telephone contact or unscheduled visit).

Duration of Study:

Approximately 2 years.

Study Endpoints:

Primary:

Safety

Safety and tolerability of multiple IV doses of ATYR1923 in patients with pulmonary sarcoidosis based on the following analyses:

• Incidence of TEAEs and serious adverse events (SAEs).

Secondary:

Potential to Decrease Background Oral Corticosteroid Dose

- Total cumulative steroid dose administered over the primary study period (Day 1 through Week 24).
- Number of patients who achieve the targeted tapered dose of prednisone 5 mg/day (or equivalent) and maintain it through Week 24.

 Exposure response analysis comparing steroid dose area under the curve (AUC) with ATYR1923 PK parameters through Week 24.

Immunogenicity

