4.1.2. Treatment Period

The treatment period consists of 6 administrations of study drug via IV infusion every 4 weeks for a total of 20 weeks of treatment (at Day 1 and Weeks 4, 8, 12, 16, and 20). Study drug will be administered by qualified study center personnel at scheduled study visits.

Between scheduled study visits, patients will be contacted by study center personnel via telephone at Weeks 1, 3, 5-7, 10, 14, and 18.

Assessments during the treatment period will be performed as presented in the Schedule of Assessments (Table 1).

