6.5. Study Completion

A patient is considered to have completed the study if they received at least 5 of 6 scheduled study drug doses and completed all follow-up visits.

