4.2.2. Secondary Endpoints

- 1) Potential to Decrease Background Oral Corticosteroid Dose
 - Time adjusted Area Under the Curve (AUC) of steroid dose administered over the study periods (Day 1 through the end of dosing interval and Day 51 through the end of dosing interval) by treatment cohort
 - Number of patients who achieve the targeted tapered dose of prednisone 5 mg/day (or equivalent) and maintain it through the end of dosing interval by treatment cohort
 - Exposure response analysis comparing steroid dose area under the curve (AUC) with ATYR1923 PK parameters through Week 24. This endpoint is not analyzed based on this analysis plan. A separate document is prepared for all PK related analyses.
- 2) Immunogenicity of multiple IV doses of ATYR1923 in patients with pulmonary sarcoidosis based on the following endpoints:
 - Incidence and titer of positive ADA (anti-ATYR1923) and anti-Jo-1 Ab.

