10.1.3. Time adjusted OCS Burden

Time adjusted AUC is a measure of steroid burden and approximates the mean steroid usage post-baseline for each patient. For each patient, it is calculated and summarized as follows,

$$Time\ Adjusted\ AUC = \sum_{t=M}^{N-1} \frac{AUC}{N-M} = \sum_{t=M}^{N-1} \frac{(C_t + C_{t'}) (t' - t)}{2(N-M)},$$

where

C_x is the OCS dose in mg on day x ,

t' is the study day of the next known OCS daily dose after day t ,

M and N are start and end study days of the analysis periods of interest. In this study, we are interested in the time periods a) Day 1 through end of dosing period (30 days after last dose) or day of last known OCS dose (if earlier than end of dosing period) and b) Day 51 through end of dosing period (30 days after last dose) or day of last known OCS dose (if earlier than end of dosing period).

Similarly, change from baseline and percent change from baseline at each diary entry will be used as C_x in the formula above, and analyses will be repeated.

aTyr Pharma, Inc.
Study ATYR1923-C-002 Statistical Analysis Plan
IND#: 133692

FINAL Version 1.0
2021-08-02

In addition, active treatment arm for each cohort and combined active arm are compared to combined placebo using the following pseudo code.

```
proc glm data = auc;  
  class treatment(ref=Placebo);  
  model auc = treatment baselineOCS / solution;  
  lsmeans treatment / pdiff=control("Placebo") adjust=T cl;  
run;
```

The difference between LS means, 95% Confidence Intervals and p-values will be presented.

Time adjusted AUC for Day 1/51 through end of treatment periods will be summarized using density and box plots by treatment.

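### The SAP analyses steroid burden only to 30 days after the last infusion; the same analysis through Week 24, the protocol's window, should be added

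*SAP*

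**What the plan says.** The protocol synopsis lists as its first secondary endpoint "Total cumulative steroid dose administered over the primary study period (Day 1 through Week 24").

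SAP 3.3 makes two changes to it.

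- **Metric.** Patients may be dosed for different lengths of time and seen on different days. "Therefore, a time adjusted AUC will be used to examine OCS use".
- **Window.** Citing the product's half-life, the SAP says "it was decided that the endpoints will be examined for the end of dosing period instead", and then: "The end of dosing period is defined as 30 days after the last dose".

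SAP 4.2.2 carries only the new version ("Time adjusted Area Under the Curve (AUC) of steroid dose administered over the study periods"), starting on Day 1 or Day 51 and running to the end of the dosing interval. SAP 10.1.3 sets the Day 1 period as "Day 1 through end of dosing period (30 days after last dose) or day of last known OCS dose", whichever comes first, and the Day 51 period ends in the same way. It then compares each active arm and the combined active arm with pooled placebo by ANCOVA on baseline OCS dose, reporting LS-mean differences, 95% confidence intervals and p-values. Under SAP 10 this is run in the mITT Set and repeated in the Efficacy Evaluable Set.

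**The concern.** The end of each patient's window is set by when that patient stopped study drug. Stopping happens after randomisation and can depend on how the patient is doing. Steroid taken more than 30 days after the last infusion cannot change the patient's value, and the mean over the shorter window stands for that patient in the arm comparison. The half-life explains an interest in the on-drug period, but it does not make stopping independent of prognosis.

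The mITT label suggests a comparison of everyone dosed over the planned study period. What is estimated is steroid burden while on treatment. The SAP already serves the on-drug question in two other ways: the Efficacy Evaluable Set requires at least four doses, and section 10.1.4 removes time around missed doses. The protocol's own question, steroid burden through Week 24, has no tabulated or modelled answer. With 8 patients per active arm, one patient's window can visibly move an arm mean.

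**Working it through.** **Inputs.** Infusions are given "at Day 1 and Weeks 4, 8, 12, 16, and 20" (Protocol 4.1.2), which the Schedule of Assessments places on Days 1, 29, 57, 85, 113 and 141. Week 24 is Day 169. A study completer is one who "received at least 5 of 6 scheduled study drug doses and completed all follow-up visits" (Protocol 6.5). Protocol 6.3.1 withdraws patients who miss two consecutive doses, after an EOS visit. The plan gives no sample-size or power figure to reproduce.

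**Formulas.** Cut = last-infusion day + 30. Days dropped if followed to Week 24 = 169 − cut, not below 0. If the patient instead leaves at the second missed infusion, 56 days after the last one, days dropped = 56 − 30 = 26. The Day 51 period to Week 24 spans 169 − 51 = 118 days.

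| Consecutive infusions | Last infusion | Cut | Dropped if followed to Day 169 | Dropped if withdrawn at second missed dose | Day 51 period kept, of 118 |
|---|---|---|---|---|---|
| 6 | Day 141 | Day 171 | 0 | not applicable | 118 |
| 5 | Day 113 | Day 143 | 26 (15%) | not applicable | 92 |
| 4 | Day 85 | Day 115 | 54 (32%) | about 26 | 64 |
| 3 | Day 57 | Day 87 | 82 (49%) | about 26 | 36 |
| 2 | Day 29 | Day 59 | 110 (65%) | about 26 | 8 |
| 1 | Day 1 | Day 31 | 138 (82%) | about 26 | none |

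A patient with five infusions who attends all follow-up visits is a protocol completer and still loses 26 in-study days.

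**Illustration from Day 51 (assumed doses).** The last infusion is on Day 57, with 5 mg/day to Day 87 and 20 mg/day afterwards.

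- SAP window: 5.0 mg/day.
- To Day 169: (36×5 + 82×20)/118 = 1,820/118 = 15.4 mg/day. The SAP's trapezoid, which averages over the day of the jump, gives 15.36.
- To Day 113 only: (36×5 + 26×20)/62 = 700/62 = 11.3 mg/day.
- Shift in the mean of an 8-patient arm: (15.4 − 5.0)/8 = 1.3 mg/day, or (11.3 − 5.0)/8 = 0.8 mg/day.

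**Illustration from Day 1 (assumed doses).** The last infusion is again on Day 57, with 15 mg/day to Day 14, 10 mg/day to Day 28, then 5 mg/day to Day 87. By the SAP trapezoid:

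- SAP window: (195 + 12.5 + 130 + 7.5 + 290)/86 = 635/86 = 7.38 mg/day, whatever follows.
- To Day 169 with the dose staying at 5 mg/day: (635 + 82×5)/168 = 1,045/168 = 6.22 mg/day.
- To Day 169 with 10, 15 or 20 mg/day after the cut: 8.65, 11.07 or 13.50 mg/day.

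On this path the SAP value is too high if the later dose is below about 7.4 mg/day and too low if it is above.

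**The case against.** The case for leaving the SAP alone has several parts.

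- **The change is open and was delegated.** Protocol 10.1.1.6 leaves the handling of early discontinuation to the SAP. SAP 3.3 declares the change and gives reasons, and SAP 3.1 says the plan is finalised before unblinding. A reader might infer an undisclosed or outcome-driven switch; nothing in the documents supports that.
- **The window has a pharmacological basis.** Protocol 2.2 gives a mean half-life of 7 to 10 days, so 30 days is about three to four half-lives (30/10 = 3; 30/7 = 4.3).
- **Rescue does not itself trigger stopping.** Protocol 7.1.6.3 keeps patients who need more steroid on blinded study drug. Increases before stopping, and for 30 days after, are counted.
- **A fixed Day 169 cut has its own fault.** If infusions run late, as Protocol 6.3.1 allows, it would drop on-treatment days.
- **Stakes are modest.** The primary endpoint is safety, there is no formal hypothesis testing (SAP 7.4.1), and p-values are exploratory (SAP 7.5).

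All of this stands and lowers the stakes, and the late-dosing point shapes the fix. None of it supplies the missing analysis.

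A reader might also infer that the protocol's quantity is reported nowhere at all. That goes too far. Daily-dose profiles are plotted with no stated truncation (SAP 10.1.6), collected data are listed (SAP 7.3.3), and a steroid AUC through Week 24 survives in the exposure-response endpoint assigned to a separate plan (SAP 4.2.2). Plots and listings are not a summary of burden, however, and that plan is not among the documents reviewed.

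**Conclusion.** The point holds as a gap in the analysis. The SAP replaces the protocol's Week 24 endpoint with a while-on-treatment mean and keeps no supporting Week 24 analysis, although it reports treatment differences with intervals and p-values.

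Two stronger readings are tempting and are not supported.

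- **That the cut favours whichever arm loses patients early.** The direction depends on the dose after the cut. A rise flatters the early leaver. If the dose stays at the 5 mg/day target, the Day 1 mean is overstated, because the short window gives more weight to the pre-taper and taper doses.
- **That 82 or 110 days of recorded steroid use will be discarded.** These are upper bounds that need follow-up to Week 24. Protocol 4.1.3 places the EOS visit at Week 24 for all patients. Protocol 6.3.1, in the COVID-19 section, withdraws patients after two missed doses, in which case about 26 days lie beyond the cut. The documents do not say how long OCS diaries continue after study drug stops.

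The day counts assume on-schedule infusions. The mg/day figures rest on assumed dose paths. No discontinuation rate is given, so the effect on the actual comparison cannot be stated.

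**What to change.** Keep the SAP version. In SAP 10.1.3 add the same ANCOVA on time-adjusted AUC for two further periods, from Day 1 and from Day 51, each running through Week 24. Define that end as the actual EOS visit day, or the last recorded OCS dose if earlier, so that late infusions do not lose on-treatment days. Use every recorded OCS dose, whether or not study drug has been discontinued.

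Report by arm:

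- the number of patients with OCS records after the 30-day cut, and the number of such days;
- the number of patients whose OCS record ends before Week 24.

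The cost is one extra run of existing code and a short table. The added analysis can use only the OCS records that exist, so patients withdrawn early stay truncated. The second count shows how far that limits the result.

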4. STUDY OBJECTIVES AND ENDPOINTS

Study objectives and endpoints defined in the protocol include safety, immunogenicity, pharmacokinetics and efficacy. Objectives and pre-specified endpoints are as follows:

4.1. Study Objectives

4.1.1. Primary Objective

To evaluate the safety and tolerability of multiple ascending intravenous (IV) doses of ATYR1923 in patients with pulmonary sarcoidosis.

4.1.2. Secondary Objectives

To assess the potential steroid-sparing effect of multiple ascending doses of ATYR1923 in patients with pulmonary sarcoidosis.

To assess the potential immunogenicity of multiple ascending IV doses of ATYR1923 in patients with pulmonary sarcoidosis.

To characterize the PK of multiple ascending IV doses of ATYR1923 in patients with pulmonary sarcoidosis. This objective and its corresponding endpoints are analyzed in a separate analysis plan.

4.1.3. Exploratory Objectives

One exploratory objective has been defined for the study as follows:

To explore the preliminary efficacy of multiple ascending IV doses of ATYR1923 in patients with pulmonary sarcoidosis by evaluating changes over time in:

- Disease activity (pulmonary parenchymal inflammation), assessed by ¹⁸F-fluorodeoxyglucose positron-emission tomography combined with computed tomography (¹⁸F-FDG-PET/CT).
- Lung function, assessed by percent predicted forced vital capacity (FVC%) and diffusing capacity of the lungs for carbon monoxide (DLco).
- Serum biomarkers, including angiotensin converting enzyme (ACE), soluble IL-2 receptor (sIL-2R), extracellular HARS, NRP2, and vascular endothelial growth factor C (VEGFC).
- State of immune cell anergy in peripheral blood mononuclear cells (PBMCs).
- Health-related quality of life scales, including the Sarcoidosis Assessment Tool (SAT), King's Sarcoidosis Questionnaire (KSQ), Leicester Cough Questionnaire (LCQ), Fatigue Assessment Scale (FAS), and the self-administered computerized Baseline/Transitional Dyspnea Indices (SAC BDI-TDI).

aTyr Pharma, Inc.
Study ATYR1923-C-002 Statistical Analysis Plan
IND#: 133692

FINAL Version 1.0
2021-08-02

- Skin lesions, for patients with cutaneous disease involvement at baseline, as assessed by Skin Physician Global Assessment (SPGA), body surface area (BSA) assessment, and the Sarcoidosis Activity and Severity Index (SASI; on a target lesion), as well as serial biopsies of non-target lesion(s) (optional at select sites).

4.2. Study Endpoints

4.2.1. Primary Endpoint

Incidence of TEAEs and serious adverse events (SAEs).

4.2.2. Secondary Endpoints

- 1) Potential to Decrease Background Oral Corticosteroid Dose
 - Time adjusted Area Under the Curve (AUC) of steroid dose administered over the study periods (Day 1 through the end of dosing interval and Day 51 through the end of dosing interval) by treatment cohort
 - Number of patients who achieve the targeted tapered dose of prednisone 5 mg/day (or equivalent) and maintain it through the end of dosing interval by treatment cohort
 - Exposure response analysis comparing steroid dose area under the curve (AUC) with ATYR1923 PK parameters through Week 24. This endpoint is not analyzed based on this analysis plan. A separate document is prepared for all PK related analyses.
- 2) Immunogenicity of multiple IV doses of ATYR1923 in patients with pulmonary sarcoidosis based on the following endpoints:
 - Incidence and titer of positive ADA (anti-ATYR1923) and anti-Jo-1 Ab.

4.2.3. Exploratory Endpoints

Change from baseline in clinical measures, including:

- FVC%
- DLco
- SUVmax as measured by ¹⁸F-FDG-PET/CT
- Health-Related Quality of Life, as assessed by the SAT, KSQ, LCQ, FAS, and SAC BDI-TDI.
- Skin lesions in patients with cutaneous involvement utilizing SPGA, body surface area assessment, and the SASI.

aTyr Pharma, Inc.
Study ATYR1923-C-002 Statistical Analysis Plan
IND#: 133692

FINAL Version 1.0
2021-08-02

Change from baseline in serum and tissue biomarkers, including but not limited to:

- ACE and sIL2R (disease serum biomarkers)
- Extracellular histidyl-tRNA synthetase (HARS), NRP2, and VEGFC (pathway serum biomarkers)
- State of immune cell anergy in peripheral blood mononuclear cells (PBMCs)
- Histopathology (skin biopsy)

aTyr Pharma, Inc.
Study ATYR1923-C-002 Statistical Analysis Plan
IND#: 133692

FINAL Version 1.0
2021-08-02

5. STUDY METHODS

5.1. General Study Design and Plan

As background for the statistical methods presented below, this section provides an overview of the study design and plan of study execution. The protocol is the definitive reference for all matters discussed in what follows.

This randomized, double-blind, placebo-controlled, study will evaluate the safety, tolerability, immunogenicity, PK, and preliminary efficacy of multiple ascending doses of IV ATYR1923 in patients with pulmonary sarcoidosis undergoing a protocol-guided oral corticosteroid (OCS) tapering regimen.

This study will consist of 3 staggered multiple dose cohorts. Each eligible patient will participate in only one cohort during the study. Within each cohort, 12 patients will be randomized 2:1 (block size of 6) to ATYR1923 (N=8) or placebo (N=4). Study drug will be administered via IV infusion every 4 weeks for a total of 6 doses (20 weeks of treatment). The follow-up study visit is scheduled for 4 weeks after the last infusion. The ATYR1923 doses levels to be evaluated are 1.0 mg/kg, 3.0 mg/kg, and 5.0 mg/kg.

Day 1 is the calendar day of first infusion.

Starting on Day 15, patients will begin a taper (reduction) in OCS (per the ATYR1923-C-002 Oral Corticosteroid Taper Guidelines) from their starting dose of 10-25 mg/day of prednisone (or equivalent) to a target dose of 5 mg/day, to be completed on or before Day 50. The OCS dose will be tapered by 5.0 mg/day every 1 to 2 weeks, depending on the starting dose. Smaller incremental titrations to the target dose of 5 mg/day by Day 50 may be implemented per Investigator judgement. Patients will be maintained at the target dose of 5.0 mg/day (or equivalent) through Week 24/End-of-Study (EOS). Optionally, further titrations in the OCS dose to below 5 mg/day may be attempted after the Week 16 visit, if determined by the Investigator to be feasible.

Patients who develop an acute worsening of symptoms or are unable to adhere to the protocol-defined OCS tapering regimen may receive 'rescue' treatment with higher OCS doses as clinically indicated. Upon resolution of symptoms, the Investigator may choose to reinstitute a taper back down to the target maintenance dose of 5 mg/day. Patients who require rescue treatment following two attempts at tapering to 5 mg/day may remain on a higher stable dose of OCS as determined by the Investigator. Patients who require an increase in OCS dose at any time in the study should continue to receive blinded study drug and followed through to the end of the study.

Dose Escalation

aTyr Pharma, Inc.
Study ATYR1923-C-002 Statistical Analysis Plan
IND#: 133692

FINAL Version 1.0
2021-08-02

Cohorts 1 through 3 will be enrolled sequentially in a staggered manner. After at least 6 patients of a given cohort have received at least 3 infusions of study drug (ATYR1923 or placebo), cumulative unblinded safety data (including but not limited to any reported adverse events (AEs), electrocardiogram (ECG) recordings, clinical laboratory values and vital signs) will be reviewed by the DSMB. Enrollment in the next scheduled (higher dose) cohort may commence after this review is completed, dose escalation is approved, and the remaining 6 patients have been randomized in the previous cohort. Dose escalation will continue in this manner until the highest planned dose level of ATYR1923 is reached, or the criteria for pausing enrollment have been met.

Criteria for Pausing Enrollment

In the event that a serious unexpected suspected adverse reaction (SUSAR) has occurred, the enrollment and initiation of study drug administration to new patients will be paused and the Sponsor will request an unblinded review by the DSMB, who will provide its recommendation to aTyr Pharma. Such recommendation may include, but is not limited to, stopping an ongoing cohort, stopping further dose escalation, continuing the study as planned, or continuing the study with modifications, such as evaluation of a lower or intermediate dose in the next cohort(s) to gain more information on safety and tolerability.

In addition, if unexpected, clinically significant trends or changes in other safety assessments are identified during routine blinded safety reviews the Sponsor may request the DSMB to similarly perform an unblinded review and provide recommendations.

The schedule for assessments and timing of events is presented in Table 1.

aTyr Pharma, Inc.
 Study ATYR1923-C-002 Statistical Analysis Plan
 IND#: 133692

FINAL Version 1.0
 2021-08-02

Table 1 Schedule of Time and Events

Study Period	Screen	Treatment													EOS
		1	1a	2	2a	3	3a, 3b, 3c	4	4a	5	5a	6	6a	7	
Visit	Study Day	D1	W1/ D8	W2/ D15	W3/ D22	W4/ D29	W5, 6, 7	W8/ D57	W10/ D71	W12/ D85	W14/ D99	W16/ D113	W18/ D127	W20/ D141	WK24/ D169
Visit Window (Days)	-28 to -1	-	-	±2	±3	±3	±2	±3	±3	±3	±3	±3	±3	±3	±3
Written informed consent	X														
Telephone Contact			X		X		X		X		X		X		
Eligibility check	X	X													
Demographics	X														
Medical history	X														
Height & weight ¹	X	X					X		X		X		X		X
Modified MRC Dyspnea Scale	X														
Physical examination ²	X										X				X
Vital signs ³	X	X		X		X		X		X		X		X	X
Pulse oximetry ⁴	X	X				X		X		X		X		X	X
12-lead ECG ⁵	X	X ⁵				X		X		X ⁵		X		X ⁵	X
Pulmonary Function Tests ⁶	X	X				X		X		X		X		X	X
DLco ⁷		X								X				X	X
Pregnancy test (females only) ⁸	X (serum)	X						X				X			X (serum)
Serum FSH ⁹	X														
Rheumatoid factor		X													
Jo-1 antibody (serum)	X			X		X		X		X		X		X	X
ADA sampling (serum) for anti-ATYR1923 antibodies ¹⁷	X			X		X		X		X		X		X	X
Safety laboratory testing (hematology, clinical chemistry)	X	X		X		X		X		X		X		X	X
Urinalysis ¹⁰	X	X		X		X		X		X		X		X	X
Coagulation laboratory testing (PT, INR, PTT)	X					X		X		X		X		X	X
Serology (HBsAg, anti-HCV, and anti-HIV 1/2 tests)	X														
Serum complement, serum tryptase, and IgE ¹¹		X													

aTyr Pharma, Inc.
 Study ATYR1923-C-002 Statistical Analysis Plan
 IND#: 133692

FINAL Version 1.0
 2021-08-02

Study Period	Visit	Screen	Treatment												EOS
			1	1a	2	2a	3	3a, 3b, 3c	4	4a	5	5a	6	6a	
Study Day	-28 to -1	D1	W1/ D8	W2/ D15	W3/ D22	W4/ D29	W5, 6, 7	W8/ D57	W10/ D71	W12/ D85	W14/ D99	W16/ D113	W18/ D127	W20/ D141	WK24/ D169
Visit Window (Days)	-	-	-	±2	±3	±3	±2	±3	±3	±3	±3	±3	±3	±3	±3
Plasma complement ¹¹		X													
¹⁸ F-FDG-PET/CT (optional) ¹²	X											X			
Skin lesion visual assessments (if applicable) ¹³	X			X		X		X		X		X		X	
Skin lesion biopsy (optional for patients at select sites) ¹⁴	X									X					
AE assessment/Concomitant medications		X	X	X	X	X	X	X	X	X	X	X	X	X	X
Randomization ¹⁵		X													
King's Sarcoidosis Questionnaire		X				X		X		X		X		X	X
Leicester Cough Questionnaire		X				X		X		X		X		X	X
Baseline/Transitional Dyspnea Indices		X				X		X		X		X		X	X
Fatigue Assessment Scale		X				X		X		X		X		X	X
Sarcoidosis Assessment Tool		X				X		X		X		X		X	X
Blood sampling (serum) for ATYR1923 PK ¹⁶		X ¹⁶		X		X		X		X		X		X ¹⁶	X
PBMC collection ¹⁸		X								X					X
Serum biomarkers ¹⁹		X								X				X	X
Infusion site examination ²⁰		X				X		X		X		X		X	
Study drug administration		X				X		X		X		X		X	
OCS Taper ²¹				X											

ADA = anti-drug antibodies; AE = adverse event; BMI = body mass index; D = Day; ECG = electrocardiogram; EOI = end of infusion; EOS = End-of-Study; ET= Early Termination; FSH = follicle stimulating hormone; HBsAg = hepatitis B surface antigen; HCV = hepatitis C virus; HIV = human immunodeficiency virus; HRCT = high-resolution computed tomography; INR = international normalized ratio; OCS = Oral Corticosteroid; PBMC = peripheral blood mononuclear cell; PD = pharmacodynamics; PET = positron emission tomography; PK = pharmacokinetics; PT = prothrombin time; PTT = partial thromboplastin time; SOI=start of infusion; W = week(s).

On dosing days, all assessments will be performed pre-dose unless otherwise specified.

- Height** only at Screening.
- Physical examination.** Full physical examinations are to be obtained at Screening, Week 12 and 24, abbreviated symptom-directed physical examination may be completed at other visits if needed.

aTyr Pharma, Inc.
Study ATYR1923-C-002 Statistical Analysis Plan
IND#: 133692

FINAL Version 1.0
2021-08-02

3. **Vital signs** are to be obtained at every visit. On study drug administration days, vital signs are to be measured pre-infusion and at 15 and 30 minutes (± 5 minutes) and at 1, 2, and 4 hours (± 15 minutes) after the start of infusion (SOI). Vital signs are to be measured before blood sample collection. Vital signs will include blood pressure (systolic and diastolic, recorded after lying supine for 5 min), heart rate, respiratory rate. Temperature is to be obtained at Screening and on dosing days at pre-dose, 60 minutes (± 15 minutes) after the SOI, and again at 4 hours (± 15 minutes) after the SOI.
4. **Pulse oximetry**: continuous pulse oximetry is to be measured on dosing days from 5 minutes pre-dose until EOI, and recorded at the same time points as vital signs. On non-dosing days pulse oximetry is to be obtained with vital sign assessments.
5. **12-lead ECG** is to be obtained at Screening, within 1-hour pre-dose on dosing days. At Day 1 and Weeks 12 and 20, an ECG is to be obtained at 4 hours (± 30 minutes) after SOI. The ECG is to be obtained after patients have been lying supine for 5 minutes.
6. **Pulmonary Function Testing** is to be performed using the same spirometer throughout the study. Parameters include forced vital capacity (FVC), forced expiratory volume in 1 second (FEV₁), FEV₁/FVC ratio at all specified visits. A minimum of 3 efforts should be obtained that meet the acceptance criteria of the American Thoracic Society or European Respiratory Society.
7. **DLco** measurements *should* be obtained after patients have been sitting quietly for 5 minutes.
8. **Pregnancy** serum tests are to be performed on all females at Screening and at Week 24/EOS. A urine pregnancy test is to be performed at other time points indicated.
9. **FSH** only required for all female patients.
10. **Urinalysis** (semi-quantitative by dipstick): microscopy is to be performed if indicated by an abnormal and clinically significant result.
11. **Serum Complement, Tryptase/Plasma Complement, and IgE** are to be collected at Day 1 pre-dose and again if an infusion related reaction (IRR) occurs.
12. **¹⁸F-FDG-PET/CT scans are optional**; patients who elect to participate agree to have imaging performed within 4 weeks prior to Day 1, and within ± 5 days of Week 16 or if early termination prior to Week 16.
13. **Skin lesion evaluation**: To be completed for patients with skin lesions present. Skin lesions will be evaluated by: Skin Physician Global Assessment (SPGA), body surface Area assessment, the Sarcoidosis Activity and Severity Index (SASI).
14. **Skin lesion biopsy**: Optional for patients with skin lesions present. A non-target lesion (ie, a lesion that is not being assessed by SASI over time) is to be selected by the Investigator for biopsy during Screening and confirmed by the patient that it had been identified by his or her private dermatologist as cutaneous sarcoidosis. Skin lesion biopsy may be obtained within 4 weeks prior to Day 1 for patients who are otherwise deemed eligible for the study and within ± 5 days of Week 12 or if early termination prior to Week 12.
15. **Randomization** is to be performed within 0-3 days prior to Day 1 or on the day of dosing.
16. **ATYR1923 serum PK** samples are to be collected pre-dose on dosing days. On Day 1 and Week 20 visits, PK samples are also collected post start of infusion at: 1 hr (just prior to [i.e., within 0-10 minutes] EOI), and at any single time point between 4-6 hours.
17. **ADA** samples are to be collected pre-dose when obtained on dosing days.
18. **Blood for PBMC assessments** will be collected pre-dose when obtained on dosing days.
19. **Serum for biomarkers** are to be collected pre-dose when obtained on dosing days.
20. **Infusion site examination**: the IV infusion site should be examined at 0.5 and 1.5 hours (± 10 minutes) after the end of infusion.
21. **OCS Taper**: OCS taper to start at Day 15 (Week 2) and continue through Day 50 (Week 7) per the ATYR1923-C-002 OCS Taper Guideline.

